STUDY PROTOCOL

TITLE: AROMATHERAPY AS AN ADJUNCTIVE THERAPY FOR NEONATAL ABSTINENCE SYNDROME

NCT: 03097484

ADDRESS: DEPARTMENT OF PEDIATRICS
DIVISION OF NEONATOLOGY
UNIVERSITY OF KENTUCKY
[name]
[name]

FUNDING: DIVISION OF NEONATOLOGY

ABBREVIATIONS: NAS, NEONATAL ABSTINENCE SYNDROME

DOCUMENT DATE: MARCH 27, 2019

STUDY BACKGROUND

The United States, Appalachia, Eastern Kentucky in particular, is in the midst of a major opioid abuse epidemic. This current epidemic is driven by misuse of prescription painkillers, i.e. Subutex and Saboxone. As prescription pills become more expensive and harder to acquire, addicts are seeking similar, cheaper drugs; such as heroin. From 1998 to 2011, the prevalence of opioid abuse and dependence amongst pregnant women has increased by 127%, from 1.7 per 1000 to 3.9 per 1000. Neonatal Abstinence Syndrome (NAS) or neonatal opioid withdrawal syndrome is a condition produces gastrointestinal and autonomic neurologic dysfunction. Infants with severe withdrawal experience dysregulation of autonomic functions, resulting in feeding difficulty, diarrhea, excessive sleepiness, and tremors. Nearly two thirds of all babies exposed to opioids during gestation will require admission to a neonatal intensive care unit for management of withdrawal symptoms. During a typical year the Neonatal Intensive Care Unit (NICU) at Kentucky Children's Hospital admits approximately 100-120 infants exhibiting NAS symptoms; these infants have a typical length of stay of 24 days if they require pharmacologic treatment.

The mainstay of treatment for NAS involves opioid replacement therapy with morphine to minimize withdrawal symptoms. Once symptoms are well controlled, the infant is said to have been "captured." At this point a slow weaning of his morphine dose occurs. The infants' clinical status is assessed with the Finnegan Scoring system, which examines symptoms such as crying, excessive sleepiness or difficulty sleeping, insomnia, or tremors along with objective findings such as temperature and respiratory rate.

In addition to pharmacotherapy, alternative and complementary medicine techniques are slowly entering the NAS treatment algorithm. Treatments such as music therapy infant massage, kangaroo care, aromatherapy, and acupressure are now employed in NICUs in addition to traditional opioids replacement. However, few studies exist in the literature to evaluate their effectiveness.

Aromatherapy is the practice of using natural essential oils to achieve a desired effect in an individual. Scents such as lavender and chamomile have been documented to have a soothing calming effect. Studies involving infants shown that lavender not only reduce crying and enhance sleep, but also reduce levels of salivary cortisol, a stress hormone. Additionally, aromatherapy is currently used as an adjunctive therapy at the University of Kentucky's Markey Cancer Center.

Salivary cortisol is a non-invasive biomarker that has proven useful for monitoring stress in neonates. It is a simple and painless method for monitoring the stress hormone cortisol. Salivary cortisol has been used successfully in infants as a method to assess infant stress associated with prone position versus supine positioning. These studies have shown that salivary cortisol levels vary with stressful or soothing stimuli.

To date, no dangerous or deleterious effects have been described from traditional inhalational use of aromatherapy or with salivary cortisol sampling. Studies have shown aromatherapy to be an effective adjunctive therapy by proving a calming effect. In our patient population it may prove to be a useful complimentary therapy ultimately reducing infant stress, hospital length of stay, and burden of opioid use. Additionally, salivary cortisol's ease of collection and non-invasive nature make it an ideal biomarker to study.

INCLUSION/EXCLUSION CRITERIA

Inclusion Criteria:

- Infants greater than or equal to 36 weeks EGA
- Intrauterine opioid exposure
- Primary diagnosis of NAS
- Parental permission to participate

Exclusion Criteria:

- Infants less than 36 weeks EGA
- Major congenital anomalies
- Latrogenic drug withdrawal
- Diagnosis of infection or respiratory distress
- Prior initiation of opioid replacement therapy
- Non-English speaking
- Infants with respiratory conditions

ENROLLMENT

Patients will be evaluated at admission or transfer to the University of Kentucky NICU and consent obtained from the mother. Patients will be randomized to one of two groups using block randomization in groups of four. The study will not be blinded (open-label).

STANDARD OF CARE AND INTERVENTION

Standard of care will include quiet environment, occupational therapy, music therapy and infant massage. Kangaroo care and breast feeding will be encouraged based on clinical recommendations.

Interventional treatment will include all aspects of the standard of care in addition to aromatherapy. Patches will be obtained from BioEsse Technologies™ and will have an 80:20 mixture of Lavender and Chamomile in a 55-microliter standard dose. When activated, each patch releases, the mixture over a 2-8 hour period by design and a

constant diffusion rate. These will be attached to a positioning device placed in the infant's bassinet 6-8 inches from the infant's nose for a period of 4 hours twice a day.

ASSESSMENT

Comfort levels will be assessed using the MOTHER-NAS scoring system. After three consecutive scores of greater than or equal to 9 or two consecutive scores of greater than or equal to 13, replacement morphine (0.05mg/kg/dose every three hours) will be initiated. After 48 hours of symptom control, morphine will be weaned by 0.02mg/day. Any significant increase in scores that accompanied the wean will induce a return to the previous dose.

DATA COLLECTION AND STATISTICAL ANALYSIS PLAN

Data will be collected from hospital electronic medical records and stored in a secure manner. Data will include: 1) date of birth, 2) date of admission, 3) birth weight, 4) gender, 5) APGAR scores, 6) mode of delivery, 7) place of birth, 8) type of prenatal drug exposure, 9) prenatal care, 10) Finnegan scores, 11) average daily heart rate, 12) daily morphine dose, 13) total morphine dose per day, 14) length of treatment, and 15) length of hospitalization.

Data will be analyzed using standard statistical techniques. The two treatment groups will be compared with a two-tailed t-test, while dichotomous variables will be examined with a Chi-Square test. Statistical significance will be set at $p=0.05$.

Anticipated CONSORT Diagram showing the flow of participants through each stage of the trial.

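### With a fixed block size of four in an open-label, single-unit trial, an enroller holding a full tally could deduce one assignment in three; hidden, varying block sizes would nearly remove this.

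*Combined protocol and SAP*

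**What the plan says.** The Enrollment section gives one block size and states in the next sentence that the trial is open: "Patients will be randomized to one of two groups using block randomization in groups of four. The study will not be blinded (open-label". Recruitment is at one unit: "Patients will be evaluated at admission or transfer to the University of Kentucky NICU and consent obtained from the mother". The plan does not give the allocation ratio, and describes no stratification, no method of generating or holding the list, and no allocation concealment. It does not say who enrols.

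Under Standard of Care and Intervention, the aromatherapy arm is recognisable at the bedside while patches are in use: "These will be attached to a positioning device placed in the infant's bassinet". Controls have the same background care without patches: "Interventional treatment will include all aspects of the standard of care in addition to aromatherapy".

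The Data Collection and Statistical Analysis Plan specifies unadjusted comparisons: "The two treatment groups will be compared with a two-tailed t-test, while dichotomous variables will be examined with a Chi-Square test".

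**The concern.** In an open-label trial, selection is protected only if nobody can foresee the next assignment when deciding whom to approach and enrol. A single block size printed in the protocol weakens that protection, because once one arm has used up its places in a block, the rest of the block is forced. One unit and unmasked care make a running tally feasible. Study Background gives 100–120 NAS admissions a year, about two a week.

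If those who approach mothers or judge eligibility also know past assignments (an assumption), three things could come to depend on the arm known to be next: whom to approach, how hard to encourage consent, and the judgement that NAS is the main diagnosis. Infant severity plausibly affects morphine dose, length of treatment and length of stay, all of which are collected. An unadjusted t-test or Chi-Square test would carry the resulting difference into the result.

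**Working it through.** The plan gives no sample size, power or predictability figure, so there is none to reproduce.

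**Inputs.** From the Enrollment section: block size 4, two arms, open label, one unit. From the analysis plan: two-sided t-test at 0.05. Assumed: 1:1 allocation, one unstratified list, and an enroller who knows the block size, the block starts and all earlier assignments.

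**Step 1: fixed blocks of four, exact.** A 1:1 block has 6 equally likely orders. In AABB and BBAA the third and fourth assignments are forced. In the other four orders only the fourth is.

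- Certain by position: 0/6, 0/6, 2/6, 6/6.
- Certain overall: (2×2 + 4×1) / (6×4) = 8/24 = 33.3%.
- Best guess correct by position: 1/2, 2/3, 2/3, 1. The mean is (0.500 + 0.667 + 0.667 + 1) / 4 = 17/24 = 70.8%.

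If the ratio were 1:3, the four possible orders would have 3, 2, 1 and 1 forced positions, so 7/16 = 43.8% would be certain.

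**Step 2: hidden varying sizes, simulated.** The enroller knows the set of sizes but not the current one. An assignment counts as certain only if every block history consistent with the tally forces it.

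| Block sizes | Certain | Best guess correct |
|---|---|---|
| 4 only | 33.3% | 70.8% |
| 2, 4 | about 11% | about 72% |
| 4, 6 | about 5.5% | about 69% |
| 2, 4, 6 | about 4.1% | about 70% |
| 4, 6, 8 | about 2.3% | about 68% |

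**Step 3: possible bias (illustration only).** Assume totals of 40, 60 and 80, an outcome with SD 1 and no true effect. The enroller shifts the outcome of the infant enrolled by −d when aromatherapy is expected next and by +d when control is expected.

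Acting only when certain, bias = 2 × d × (share certain):

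- Fixed four: 2 × 0.25 × 0.333 = 0.17 SD, and 2 × 0.5 × 0.333 = 0.33 SD.
- Sizes 4, 6, 8: 2 × 0.25 × 0.023 = 0.01 SD, and 2 × 0.5 × 0.023 = 0.02 SD.

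Acting on every best guess, bias = 2 × d × (2 × share correct − 1):

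- Fixed four: 2 × 0.25 × 0.417 = 0.21 SD, and 2 × 0.5 × 0.417 = 0.42 SD.
- Sizes 4, 6, 8: 2 × 0.25 × 0.36 = 0.18 SD, and 2 × 0.5 × 0.36 = 0.36 SD.

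Simulated false-positive rates of the two-sided t-test, as ranges over the three totals (nominal 5%):

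| Enroller acts | d | Fixed 4 | Hidden 4, 6, 8 |
|---|---|---|---|
| Only when certain | 0.25 | 8–11% | about 5% |
| Only when certain | 0.5 | 16–30% | about 5–6% |
| On every best guess | 0.25 | 9–15% | 8–12% |
| On every best guess | 0.5 | 23–41% | 17–31% |

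**Step 4: balance.** Fixed fours can be out by at most 2 infants, and by 0 when the total is a multiple of four. With 4, 6, 8 the maximum is 4 and the simulated mean is about 0.6.

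**The case against.** The strongest reply is that the arithmetic is right but the harm needs a long chain of conditions.

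- **The tally.** Patches are in place for 4 hours twice a day, in one arm only. At the bedside a control looks like a non-participating infant with NAS. The patch therefore does not reveal control assignments, enrolment order or block boundaries; a full tally also needs the study log or good recall. This stands. Open-label conduct in one unit makes a tally feasible, but the documents do not show that any enroller has one. Nor does silence on concealment show that there is none.
- **Room to steer.** Evaluation is tied to admission or transfer and most criteria are objective. Delay risks losing the infant to the exclusion "Prior initiation of opioid replacement therapy". This stands too.
- **Size of the shift.** Suppose steering means refusing one tail of a normal prognosis score. If prognosis predicted outcome perfectly, a 0.25 SD shift would require refusing about 13% of candidates at certain positions, and 0.5 SD about 30%. At a prognosis–outcome correlation of 0.5 these become about 30% and 62%, and at 0.3 about 52% and 88%. The 0.5 SD rows are therefore an extreme case.
- **Limited remedy.** Against an enroller who acts on guesses, varying sizes help only modestly. This is true; the benefit claimed is the removal of certainty.

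None of this touches the predictability result. Concealment alone is not an answer either, since sealed or central release cannot hide an assignment that follows from those before it.

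**Conclusion.** The concern holds as a design weakness that should be corrected. Under 1:1 allocation and a fully informed enroller, exactly one third of assignments over complete blocks are certain, and hidden sizes of 4, 6 and 8 cut this to about 2.3%. Confidence in those figures is high. Whether bias would follow is much less certain. It depends on who enrols, what they know and how far they could act on it, none of which the documents give. The false-positive rates show what steering could do under assumed sample sizes and shifts; they are not estimates for this trial.

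**What to change.** For all assignments still to be made, replace the fixed block of four with block sizes varied at random, for example 4, 6 and 8. Do not disclose the sizes to enrolling staff, and keep them out of the protocol. Avoid 2 as the smallest size: the set 2 and 4 is slightly easier to guess than fixed fours. As supporting practice, hold the list away from enrolling staff and release each assignment only after consent and eligibility are recorded.

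The cost is regenerating the remainder of the list and accepting the small imbalance shown above. No extra infants, visits or changes to care are needed. Enrolment status is not given, so the benefit is limited to infants not yet randomised; assignments already made stay as they are.

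Suggested wording: *Allocation will use permuted blocks of randomly varying size. Block sizes will be held in a restricted document not available to staff who enrol participants. Each assignment will be released only after consent and eligibility have been recorded.*

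### No score defines the rise that reverses the morphine wean, and none is stated for starting it, so in this open-label trial the same scores could lead to different dosing by arm

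*Combined protocol and SAP*

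**What the plan says.** The Assessment section states that "Comfort levels will be assessed using the MOTHER-NAS scoring system" and ties the start of morphine to "three consecutive scores of greater than or equal to 9 or two consecutive scores of greater than or equal to 13". The wean is described next: "After 48 hours of symptom control, morphine will be weaned", in steps of 0.02 mg/day. Reversal is covered by one sentence: "Any significant increase in scores that accompanied the wean will induce a return to the previous dose".

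The only other description of control is in Study Background, where "Once symptoms are well controlled, the infant is said to have been" captured, again without a score.

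On masking, Enrollment says "The study will not be blinded (open-label". No masked scorer, independent dosing decision or sham patch is described. The data list includes scores, daily morphine dose, length of treatment and length of hospitalization. No primary outcome is named, but Study Background hopes for a therapy "ultimately reducing infant stress, hospital length of stay, and burden of opioid use".

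**The concern.** Three decisions govern an infant's course on morphine: starting it, beginning the wean and reversing a reduction. Only the first has a score. The other two largely determine how much morphine is given and for how long, and they can affect length of stay. These are the benefits the investigators hope to see.

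The patch sits in the bassinet near the infant for two four-hour periods a day, and controls have no described counterpart. Bedside staff therefore probably know the arm. This is an inference, since the plan does not say who scores or who doses. Where a trigger is left to judgement, a person who knows the arm may tolerate a rise in one arm and reverse the wean for the same rise in the other. A difference between arms could then reflect handling rather than the patch, and a two-tailed t-test cannot tell these apart.

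**Working it through.** The plan states no sample size, power, effect size or standard deviation, so there is no figure to reproduce. The check compares the texts and adds a small count.

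**1. The three triggers side by side (Assessment)**

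| Decision | Condition | Score criterion |
|---|---|---|
| Start morphine | Consecutive high scores | Three of 9 or more, or two of 13 or more |
| Begin the wean | 48 hours of control | None stated |
| Reverse a reduction | Significant rise in scores | None: no size, cut-off, number of scores or time window |

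No other section fills the two empty cells. The text also does not say whether the 48 hours restart after a reversal.

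**2. Whether reasonable readings lead to different doses for the same scores**

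- Reading A: control means the start criterion is not met, and a reversal follows when it is met again.
- Reading B: control means no score of 9 or more, and a reversal follows two consecutive scores of 9 or more or any single score of 13 or more.

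Take an infant who repeatedly scores 12, 12, 8. The longest run of scores of 9 or more is two, and none reaches 13, so the start criterion is never met. Under A this infant counts as controlled, is weaned and is never stepped back. Under B the wean does not begin, and the same pattern after a reduction causes a step-back. A single score of 20 among scores below 9 causes no step-back under A and a step-back under B. The protocol's wording excludes neither reading.

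**3. How often the undefined trigger is met**

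Assume a weight of 2.5 to 4.0 kg (not in the documents), weaning from the starting dose, and no reversals.

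- Starting dose: 0.05 × 2.5 = 0.125 mg to 0.05 × 4.0 = 0.20 mg per dose. With eight doses a day, this is 1.0 to 1.6 mg/day.
- If 0.02 mg comes off each dose daily: 0.125 / 0.02 = 6.25, so 7 steps, to 0.20 / 0.02 = 10 steps.
- If 0.02 mg comes off the daily total: 1.0 / 0.02 = 50 to 1.6 / 0.02 = 80 steps.

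The protocol does not say which is meant. On either reading, a treated infant passes the undefined reversal trigger many times.

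**4. Size**

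A shift in mean treatment length would need two quantities: the difference between arms in reversals per infant, and the delay per reversal. The documents give no basis for the first. The second has no upper limit if the 48 hours restart, because that clock can begin only once control is regained. No figure in days is therefore offered.

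**The case against.** **Control has a natural meaning.** The start thresholds come one sentence before the wean rule, and a reader could take control to mean scores below them. This stands in part, and that gap is the softer of the two. The reading is unstated, it can mean either A or B above, and it leaves a significant increase undefined.

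**The data permit a check afterwards.** Scores and daily doses are both collected, so the scores preceding each wean and each reversal can be compared by arm. This stands: a reader might infer that differential handling could never be detected, and the data list does not support that. The check is only partial, because the scores may themselves be influenced by knowledge of the arm. It also needs the collected scores to be the dosing scores. Assessment doses on MOTHER-NAS, while the data list collects Finnegan scores, the system named in Study Background ("clinical status is assessed with the Finnegan Scoring system, which examines symptoms such as crying"), and the two are not said to be the same.

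**A score rule closes only one route.** Unmasked staff can still influence the score, and the numeric start rule is equally exposed. The plan also gives no rule for escalating or stopping morphine, or for discharge. All of this stands and limits what the fix can achieve.

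**No bias is shown.** This also stands. A reader might infer that the plan favours aromatherapy, or that treatment length would be off by some number of days. The documents support neither: the direction is open, the rater is unnamed, and the size cannot be calculated.

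**Conclusion.** The concern holds as a gap in the dosing rules. The trigger for reversing the wean has no score or other anchor, and the trigger for starting it has a duration but no stated score. Combined with open-label care, this lets the same scores lead to different doses by arm, with possible effects in either direction on morphine dose, length of treatment and length of hospitalization. Only infants who receive morphine pass through these decisions.

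The conclusion rests on one inference, that the staff making the decisions know the arm. It does not rest on the assumed weights, which only illustrate how often the decision recurs. The gap should be closed, but it does not by itself invalidate a comparison. With no primary outcome named, it also cannot be said whether a primary result is affected.

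**What to change.** Before enrolment, write both triggers as score rules on the scale used for dosing, and apply them identically in both arms. For example:

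- **Begin the wean** after 48 hours with no score of 9 or more.
- **Step back** after two consecutive scores of 9 or more, or any single score of 13 or more.
- **Cut-offs** to be confirmed by the clinical team. Reusing the start criterion unchanged is not advised, because it would treat the 12, 12, 8 pattern as controlled.
- **Restart:** say whether the 48 hours begin again after a step-back.
- **Override:** allow one on clinical grounds, recorded with its reason.
- **Reporting:** give step-backs and overrides by arm. As a partial check, compare by arm the scores preceding each wean and step-back, having confirmed that the collected scores are those used for dosing.

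The cost is a few sentences of protocol wording, one data item beyond the 15 listed (the override and its reason), a short table and slightly less bedside discretion. The report should state the remaining limitation: the rule constrains dosing for a given score, but bias from unmasked scoring and from discretionary stopping and discharge decisions remains.

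### Should the morphine comparison be adjusted for birth weight instead of resting on the planned unadjusted t-test?

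*Combined protocol and SAP*

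**What the plan says.** The section on data collection and statistical analysis gives one rule for all comparisons: "The two treatment groups will be compared with a two-tailed t-test, while dichotomous variables will be examined with a Chi-Square test". No regression, covariate or stratified analysis is mentioned. Under Enrollment, "Patients will be randomized to one of two groups using block randomization in groups of four", with no stratification factor named.

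The collected data begin with "1) date of birth, 2) date of admission, 3) birth weight" and include "12) daily morphine dose, 13) total morphine dose per day". Neither morphine item carries a unit, and no single morphine figure per infant is defined.

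Under Assessment, once the score thresholds are met, "replacement morphine (0.05mg/kg/dose every three hours) will be initiated"; later "morphine will be weaned by 0.02mg/day". An infant who never reaches a threshold gets no morphine under this rule. The exclusion list contains "Prior initiation of opioid replacement therapy", so every infant enters untreated.

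The background hopes that aromatherapy may help in "ultimately reducing infant stress, hospital length of stay, and burden of opioid use". No outcome is labelled primary, and no sample size or power is stated.

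**The concern.** The starting dose is per kilogram, so among treated infants the starting amount in mg is proportional to dosing weight. Birth weight is a close proxy for dosing weight, is fixed before randomisation and is already on the data list. An unadjusted comparison of mg leaves the weight-driven spread in the error term.

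A linear model on arm and birth weight could remove that spread at the price of one degree of freedom and one sentence in the plan. In a small trial a few points of power may matter. In an open-label trial, a covariate chosen after the data are seen would carry little credibility. Opioid burden is one of the hoped-for benefits, so the idea deserved a check.

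**Working it through.** **Inputs from the documents.** Starting dose 0.05 mg/kg every three hours; two-tailed test at 0.05; two groups in blocks of four. There is no planned figure to reproduce, because no N, SD, effect size or correlation is given.

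**Assumptions.** Mean weight 3.0 kg with CV 15% (CVw = 0.15); residual CV of morphine amount 30, 60 or 100% (CVe); share of infants ever treated p = 100, 85, 70 or 50%; 20 or 30 infants per arm, allocated 1:1.

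**Step 1: the weight link.** 0.05 × 8 = 0.4 mg/kg/day. At 2.5, 3.0 and 3.5 kg that is 1.0, 1.2 and 1.4 mg/day, a 40% range. The link is real in mg. In mg/kg the starting dose is the same for every infant.

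**Step 2: how much variance birth weight could explain.** If mg scales with weight and untreated infants count as zero,

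R² = CVw² / [(1 + CVw²)(1 + CVe²)/p − 1].

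For p = 1 and CVe = 0.3: 0.0225 / (1.0225 × 1.09 − 1) = 0.0225 / 0.1145 = 19.6%. In full:

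| Ever treated | CVe 30% | CVe 60% | CVe 100% |
|---|---|---|---|
| 100% | 19.6% | 5.8% | 2.2% |
| 85% | 7.2% | 3.5% | 1.6% |
| 70% | 3.8% | 2.3% | 1.2% |
| 50% | 1.8% | 1.3% | 0.7% |

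**Step 3: break-even.** One covariate inflates the variance by about 1 + 1/(N − 4), so it pays only if R² exceeds 1/(N − 3). That is 1/37 = 2.7% at N = 40 and 1/57 = 1.8% at N = 60. At 20 per arm, 7 of the 12 cells fall below break-even. At 30 per arm 4 do, and a fifth (50% treated, CVe 30%) sits on the line.

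**Step 4: power.** The settings above were simulated with 10,000 runs per cell: birth weight 3.0 kg (SD 0.45), dosing weight differing from it by about 5%, a lognormal residual, zeros for untreated infants, and a proportional treatment effect giving the t-test about 80% power. A proportional effect keeps untreated infants at zero; a fixed mg reduction would push them below zero. The linear model with HC2 robust standard errors gained about 7 points when all infants were treated and CVe was 30%. In every other cell it gained at most about 2 points, and in about half of the 24 cells it lost up to 1.2.

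**Step 5: the simpler alternative.** Dividing the amount by birth weight and keeping the t-test removes the weight term directly. Under proportional scaling, and ignoring the small gap between birth weight and dosing weight, the squared CV falls from (1 + CVw²)(1 + CVe²)/p − 1 to (1 + CVe²)/p − 1. The relative cut is R² × (1 + CVe²)/p, which always exceeds R² and costs no degree of freedom:

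- p = 1, CVe = 0.3: 19.6% × 1.09 = 21.4%.
- p = 0.5, CVe = 1.0: 0.73% × 4 = 2.9%, where the covariate removes only 0.7%.

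In the simulation the mg/kg t-test beat the adjusted model in all 24 cells, by about 1 to 2 points. Choosing mg therefore brings in a weight dependence that the model then removes only in part.

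This ranking is not universal. If amount in mg were unrelated to weight, dividing by weight would add noise. With p = 1 and CVe = 0.3 the squared CV would rise from 0.09 to about 0.1145, or by 27%, whereas the needless covariate costs only about 1 power point. The documents do not say which situation applies.

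**The case for a change.** The strongest reply is that the payoff is lopsided: perhaps several points gained against about one lost, for one sentence and no new data. The case is better still if the outcome is cumulative mg and the wean step is an absolute amount off each dose. Assume 48 hours at the starting dose, weaning to zero and no returns to a previous dose. Total mg is then 0.8w + 0.5w², or 5.1, 6.9 and 8.9 mg at 2.5, 3.0 and 3.5 kg, a 74% range. Simulated gains for a fixed mg reduction were then 0.8 to 13 points with all infants treated, 0.5 to 6 with 85% treated and 0 to 3 with 50 to 70% treated. Dividing by weight does not fully remove the dependence here, since 0.8 + 0.5w remains.

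The arithmetic stands, but it rests on one reading of the wean text. Taken off the daily total, a step of 0.02 mg takes 1.2/0.02 = 60 days at 3 kg, against a typical stay of 24 days in the background section. Taken off each dose, it takes 0.15/0.02 = 7.5 days. The starting dose, the wean step and the typical stay must be reconciled by the sponsor. Until then, a benefit that depends on one reading is not established. The range also assumes no returns to the previous dose, which the protocol allows and which would add variation unrelated to weight.

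It is also true that the unit and a single morphine figure per infant are not written down. That is missing detail about the outcome. It does not make the planned test wrong, and it has to be settled before anyone can say whether birth weight belongs in a model.

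**Conclusion.** The concern does not hold. The planned t-test gives a valid comparison of the randomised groups, with no bias; in the simulations its type I error was 4.0 to 5.3%, the same range as the adjusted model with HC2 errors. What remains is a possible precision gain for one outcome that is not a declared endpoint, in a unit the plan has not chosen.

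Under proportional scaling that gain is about 7 power points in the most favourable corner, at most about 2 elsewhere, and slightly negative in about half the settings. If morphine is analysed per kilogram, or many infants never start it, little or nothing is gained. Larger gains need cumulative mg and one particular reading of the wean text.

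These sizes rest on the assumed weight CV, residual CV, share treated and 20 to 30 infants per arm; the documents supply none of them. Adjusted mg, mg/kg with a t-test, and the t-test as planned are all defensible, and reasonable statisticians would differ. No change to the plan is called for on this point.

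### Continuous outcomes are compared by an unadjusted t-test with no stratification; prespecified adjustment for a pre-randomisation withdrawal score and drug exposure would probably add precision, by an amount the documents cannot fix

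*Combined protocol and SAP*

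**What the plan says.** The analysis plan is very short. In the section on data collection and statistical analysis, "The two treatment groups will be compared with a two-tailed t-test" and "dichotomous variables will be examined with a Chi-Square test". No regression, covariate, change from baseline or stratified analysis appears.

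On allocation, the Enrollment section says "Patients will be randomized to one of two groups using block randomization in groups of four". No stratification factor is named.

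The list of data from the electronic record includes "8) type of prenatal drug exposure, 9) prenatal care, 10) Finnegan scores". It defines no baseline score, does not say when scores are taken relative to randomisation, and contains no randomisation or patch time.

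The eligibility criteria require NAS as the primary diagnosis and exclude infants already started on opioid replacement. Under Enrollment, "Patients will be evaluated at admission or transfer to the University of Kentucky NICU". Under Assessment, consecutive high scores start morphine, and later scores govern the wean.

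**The concern.** Blocks of four keep the arms equal in number. They do nothing for severity or drug exposure. With an unadjusted test as well, neither the design nor the analysis takes account of how severe withdrawal is at entry.

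The protocol's own rules make entry severity a plausible predictor of outcome. Scores decide whether morphine starts and how it is weaned, so morphine dose and length of treatment follow partly from scores. A score charted before randomisation is an early value of the measure behind those outcomes and, given the exclusion criterion, is not yet altered by replacement opioid. Type of exposure is fixed before birth and cannot be affected by arm.

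Two things are at stake. One is precision: variation that the baseline explains stays in the error term. The other is the realised sample: if one arm happens to start with sicker infants, the estimate carries that difference. In an open-label trial, an adjustment added after the data are seen would be open to challenge, so it needs to be prespecified.

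**Working it through.** **Inputs.** From the documents: two groups, blocks of four, unadjusted two-tailed t-test, significance level 0.05. Assumed, because the documents give none of them: 1:1 allocation, infants per arm *n*, standardised effect *d*, and baseline-outcome correlation *r*. The plan states no sample size or power, so there is no figure to reproduce.

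**1. Residual variance.** Adjustment multiplies it by 1 − r².
- r = 0.3: 1 − 0.09 = 0.91, a 9% reduction, equivalent to 1/0.91 = 1.10 times as many infants.
- r = 0.5: 1 − 0.25 = 0.75, a 25% reduction, equivalent to 1/0.75 = 1.33 times as many.

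**2. The same in sample size.** For 80% power, n per arm = 2(1.960 + 0.842)²(1 − r²)/d². At d = 0.5 this gives 63 unadjusted, 58 at r = 0.3 and 48 at r = 0.5. At a fixed 63 per arm, power goes from 80% to 84% and 90%. These figures ignore the degrees of freedom spent, which matter in a small trial, hence step 3.

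**3. Simulated power at d = 0.6.** The first model has a baseline score and one two-level exposure term. The second is less favourable: four exposure levels with no effect of their own, and 20% of baseline scores missing and handled by an indicator.

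| Model | n per arm | r | t-test | ANCOVA |
|---|---|---|---|---|
| Two covariates | 20 | 0 | 46% | 43.8% |
| Two covariates | 20 | 0.3 | 46% | 47.4% |
| Two covariates | 20 | 0.5 | 46% | 54.5% |
| Two covariates | 40 | 0 | 75–76% | 74.7% |
| Two covariates | 40 | 0.3 | 75–76% | 78.7% |
| Two covariates | 40 | 0.5 | 75–76% | 84.9% |
| Four levels, 20% missing | 20 | 0.3 | 45.7% | 43.2% |
| Four levels, 20% missing | 20 | 0.5 | 45.0% | 48.0% |
| Four levels, 20% missing | 40 | 0.3 | 74.5% | 74.9% |
| Four levels, 20% missing | 40 | 0.5 | 75.4% | 81.7% |

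Repeat runs agreed to within about two points. Type I error of the two-covariate ANCOVA stayed at 4.9% to 5.2%.

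**4. Chance imbalance.** The difference in a standardised baseline score has standard error √(2/n). At 20 per arm this is 0.316, so a gap of at least 0.5 SD has probability 2[1 − Φ(0.5/0.316)] = 11%. At 30 per arm it is 5%, and at 50 it is 1%. For an exposure type with 30% to 50% prevalence, a gap of 20 percentage points or more has probability 23% to 27% at 20 per arm and 12% to 16% at 30.

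**5. Effect of a gap.** A 0.5 SD gap moves the unadjusted difference by r × 0.5 SD: 0.15 SD at r = 0.3 and 0.25 SD at r = 0.5. At 20 per arm, the type I error conditional on that gap is 6.5% and 8.9%. With a gap of 0.25 SD it is 4.6% and 3.9%, below 5%. The test is right on average and off in particular samples.

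**The case against.** The strongest reply is that this is a preference for efficiency, not an error. Randomisation makes the unadjusted t-test valid, and its standard error already allows for imbalance averaged over randomisations. That stands. A reader might infer that the planned test is biased or has an inflated error rate; step 5 shows that this is true only conditionally on a particular imbalance.

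A reader might also infer that every continuous outcome would have a narrower interval after adjustment. The documents give no correlation for any outcome, and the table shows losses when the covariates carry no information or too many terms are fitted. That objection stands too, and is why exposure should be coded coarsely.

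A third tempting reading is that a score before the first patch is ready to use. The list says only "10) Finnegan scores", with no timing. Some infants arrive by transfer, so earlier scores may lie outside this hospital's record. More seriously, a score taken before the first patch can still fall after randomisation. With caregivers aware of the arm, adjusting for it could introduce a bias that the t-test does not have. Only a score charted before randomisation is safe.

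Finally, the plan names no primary outcome and no summary of repeated scores, and infants who never start morphine may have no length of treatment. These gaps need settling in their own right. They affect the t-test as much as ANCOVA and do not remove the case for a baseline covariate.

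**Conclusion.** The point holds as a worthwhile improvement in precision and protection against chance imbalance, not as a fault in validity. The plan ignores entry severity and exposure type in both allocation and analysis, while listing data from which both could be drawn.

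The size is illustrative. Under an assumed correlation of 0.3 to 0.5, residual variance falls by 9% to 25%. With two covariates and d = 0.6, power rises by about 1 to 9 points at 20 per arm and 3 to 9 at 40. With more exposure levels and missing scores, the gain at r = 0.3 disappears. If the two covariates predict nothing, the loss is about 1 point at 40 per arm and 2 at 20. The conclusion assumes that a score is charted before randomisation for most infants, which the documents make likely but do not state.

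**What to change.** For continuous outcomes, including the morphine dose variables, prespecify ANCOVA with three terms:
- treatment arm;
- the last withdrawal score charted before randomisation, defined identically in both arms;
- prenatal drug exposure in two or three categories, fixed in advance.

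Use no score taken after randomisation as the baseline. Where no eligible score exists, add a missing-indicator so that every randomised infant stays in. Because the baseline precedes randomisation, its absence cannot depend on arm. Do not require a pre-patch heart rate: only a daily average is listed, and the day of entry may already include patch time. State which instrument supplies the baseline, since the Assessment section names the MOTHER-NAS system and the data list names Finnegan scores. Report the unadjusted t-test beside the adjusted estimate.

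The cost is a short addition to the analysis plan, one new data item (the time of randomisation) so that the baseline score can be identified, and a few degrees of freedom. That is about 1 to 2 points of power if the two simulated covariates are not prognostic, and somewhat more with extra exposure categories or the indicator. No change to care or sampling is needed.
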